### **7.3. Body Weight, Height, and Vital Signs**

Descriptive statistics will be provided indication for body weight, height, body mass index (BMI), and vital signs as follows:

- Baseline value
- Values at each postbaseline time point
- Postbaseline minimum value
- Change from baseline at each postbaseline time point

A baseline value will be defined as the last available value collected on or prior to the date/time of first dose of study drug. Change from baseline to a postbaseline visit will be defined as the postbaseline value minus the baseline value. Body weight and vital signs measured at unscheduled visits will be included for the baseline value selection.

In the case of multiple values in an analysis window, data will be selected for analysis as described in [Section 3.8.3](#). No formal statistical testing is planned.

A by-participant listing of vital signs will be provided by participant ID number and time point in chronological order. Body weight, height, and BMI will be included in the vital signs listing, if space permits. If not, they will be provided separately.

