### 1.3. Schedule of Activities

**Table 1 Schedule of Activities**

Visit Name	Screening	Treatment Period				Follow-Up		Notes
		Baseline	Weeks 1, 2, 3, etc.	Early Termination*	EOT/Delivery	F1	F2 (EOS)	
Day/Week (Window)	Day -10 to -1	0*	Every 7 Days (±1 Day) Until Delivery		Day of Delivery (+2 Days)	Phone Call: 14 Days after Delivery (±3 Days)	Clinic Visit: 28 Days after Delivery (±3 Days)	
*Participants who early terminate from study drug should still continue with weekly visits through delivery, F1, and F2.
 
Some visits may be conducted as a home health or remote visit at the discretion of the investigator upon approval by the sponsor or designee and in accordance with local and regional regulations.
 
*See Section 8.1.8 for further details on timing of baseline visit.

Administrative Procedures								
Informed consent	X							
Eligibility Procedures								
Inclusion/exclusion criteria	X	X						
Demography	X							
Prior/concomitant treatment	X	X	X	X	X	X	X	
Medical history	X	X						Includes menstrual and obstetric history
Estimated gestational age assessment	X							Confirmation of eligibility based upon estimated gestational age required before randomization: CRL from early ultrasound or head circumference on ultrasound if CRL is >84 mm.

Visit Name	Screening	Treatment Period				Follow-Up		Notes
		Baseline	Weeks 1, 2, 3, etc.	Early Termination*	EOT/Delivery	F1	F2 (EOS)	
Day/Week (Window)	Day -10 to -1	0*	Every 7 Days (±1 Day) Until Delivery		Day of Delivery (+2 Days)	Phone Call: 14 Days after Delivery (±3 Days)	Clinic Visit: 28 Days after Delivery (±3 Days)	*Participants who early terminate from study drug should still continue with weekly visits through delivery, F1, and F2.  Some visits may be conducted as a home health or remote visit at the discretion of the investigator upon approval by the sponsor or designee and in accordance with local and regional regulations. *See Section 8.1.8 for further details on timing of baseline visit.
Hepatitis and HIV screen, TSH	X							If HIV results are documented as negative from the current pregnancy in a participant deemed to be low risk by the investigator, HIV at screening visit may be waived.
Dosing Procedures								
Randomization		X						
Study drug dispensing		X	X					As needed
Study drug collection/reconciliation			X	X	X			As needed
Efficacy Procedures								

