This study assesses the primary efficacy endpoint at 3 weeks because it is clinically relevant as a timeframe within which demonstrated efficacy of a drug for ICP will be important for clinical decision making. In a large population-based, case-control study (Geenes et al. 2014), 669 patients with a singleton pregnancy were identified within the UK Obstetric Surveillance System (UKOSS) as having severe ICP; the mean gestational age was 33 weeks 4 days at time of diagnosis in these patients. Additionally, in a recent double-blind, multicenter, randomized placebo-controlled study that enrolled 605 women with ICP in the United Kingdom (Chappell et al. 2019), the median gestational age was 34.4 weeks at randomization. With the mean/median gestational ages at diagnosis occurring between 33 and 34 weeks—and with Royal College of Obstetricians and Gynaecologists (RCOG) guidelines (2011) recommending consideration of elective delivery for patients with ICP after 37 weeks based on sBA-related risks of stillbirth—approximately 3 weeks of study drug treatment corresponds to a timeframe within which demonstration of sBA reduction is expected to be impactful for clinical decision making. Furthermore, based on clinical experience with another IBAT inhibitor (maralixibat),

continued improvements in sBA are likely to be seen with relatively longer treatment durations, arguing against analysis of sBA prior to the 3-week timeframe as a primary efficacy endpoint. In Study LUM001-501, decreases in both sBA and ItchRO (observer) were observed at Week 2 and continued to decline even further at Week 4 in pediatric participants with non-truncating PFIC2, supporting the benefit of treatment durations >2 weeks for reduction of sBA and pruritus. However, given the mean/median gestational ages for ICP diagnosis (33–34 weeks), along with the requirement for randomization no later than 36 weeks 0 days in Part 2, participants are relatively more likely to be at the upper range of gestational age eligibility in this study, and as such, relatively few participants in this study will be expected to remain on treatment beyond 3 weeks.

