## 9. SAFETY REPORTING

### 9.1. Safety Parameters and Definitions

#### 9.1.1. Adverse Events

An AE is any untoward medical occurrence in a patient or clinical study participant or the newborn, temporally associated with the use of study drug, whether or not considered related to the study drug. NOTE: An AE can therefore be any unfavorable and unintended sign (including an abnormal laboratory finding or vital sign), symptom, or disease (new or exacerbated) temporally associated with the use of study drug. For the AE collection period, see the SoA (Table 1) and Section 8.3.1.

This includes the following:

- Any abnormal laboratory test results (hematology, clinical chemistry, or urinalysis) or other safety assessments (e.g., radiological scans, vital signs measurements), including those that worsen from baseline, considered clinically significant in the medical and scientific judgment of the investigator (i.e., not related to progression of underlying disease).
- Exacerbation of a chronic or intermittent preexisting condition including either an increase in frequency and/or intensity of the condition
- New conditions detected or diagnosed after study drug administration even though it may have been present before the start of the study

The following events are NOT considered an AE:

- Any clinically significant abnormal laboratory findings, vital signs or other abnormal safety assessments that are associated with the underlying disease, unless judged by the investigator to be more severe than expected for the participant's condition

- An investigational abnormality (e.g., laboratory parameter, vital sign, or ECG) unless the abnormality is considered clinically significant by the investigator based on at least 1 of the following criteria:
  - Induces clinical signs or symptoms
  - Requires active intervention (including referring a participant to a specialist)
  - Requires interruption or discontinuation of study drug
- The disease/disorder being studied or expected progression, signs, or symptoms of the disease/disorder being studied, unless more severe than expected for the participant's condition. Adverse perinatal events that are included in the key secondary composite endpoint should not be captured as AEs or SAEs because they will already be captured as endpoints for the purposes of efficacy assessment.
- Medical or surgical procedure (e.g., endoscopy, appendectomy): the condition that leads to the procedure is the AE

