#### **10.4.2.3. Laboratory Assessments**

Clinical safety laboratory values will be measured by a central laboratory and, where grading criteria apply, will be graded according to the CTCAE grading scale. Summary statistics for actual values and for changes from baseline will be tabulated for laboratory results by scheduled visit. Graphs of laboratory values over time may also be produced.

Participants with clinical laboratory values outside of the normal reference range at any postbaseline assessment will be summarized, including by the CTCAE and, if necessary, other grading scales. Shifts from baseline laboratory values will be tabulated. The observed vital sign data, the change from baseline, and those meeting criteria for potentially clinically significantly abnormal criteria for each measurement will be summarized with descriptive statistics.

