### 3.8.2. Analysis Visit Windows

Participant visits might not occur on protocol-specified days. Therefore, for the purpose of analysis, observations will be assigned to analysis windows. A notable exception to the analysis visit windows below is the end of treatment/date of delivery. This will be summarized as its own visit and that will be the value used for endpoints that look at either the value or change from baseline to delivery.

The analysis windows for ItchRO, sBA, hematology, chemistry, coagulation, weight, vital Signs, and urinalysis are provided in [Table 2](#).

The analysis windows for 5-D Itch, EQ-5D-5L, PROMIS Fatigue and Sleep patient reported outcomes (PROs), PIS-Itch, PGIC-Itch, and Biomarker samples (7 $\alpha$ -hydroxy-cholesten-3-one [7 $\alpha$ C4], fibroblast growth factor 19 [FGF-19], autotaxin, progesterone sulfate, and glucagon-like peptide 1 [GLP-1]) are provided in [Table 3](#).

The analysis windows for lipid panel and glycated albumin are provided in [Table 4](#).

The analysis windows for vitamin A, D, and E levels and fetal ultrasound are provided in [Table 5](#).

**Table 2 Analysis Visit Windows for ItchRO^, sBA, Hematology\*, Chemistry\*, Coagulation\*, Weight, Vital Signs, and Urinalysis**

Nominal Visit	Nominal Study Day	Lower Limit	Upper Limit
Baseline	1	(none)	1
Week 1	8	2	11
Week K (K is every week after previous visit)	K*7 + 1	K*7 – 2	K*7 + 4

^ ItchRO is collected daily, but will have weekly averages calculated and results will be grouped according to the analysis windows above.

\* Hematology, chemistry, and coagulation are not planned to be collected at the baseline visit. Rather, the screening visit (or a subsequent unscheduled visit) will serve as the baseline.

**Table 3 Analysis Visit Windows for 5-D Itch, CSS, EQ-5D-5L, PROMIS Fatigue and Sleep PROs, PIS-Itch, PGIC-Itch, and Biomarker Samples (C4, FGF-19, Autotaxin, Progesterone Sulfate, GLP-1)**

Nominal Visit	Nominal Study Day	Lower Limit	Upper Limit
Baseline*	1	(none)	1
Week 3	22	19	25

\*PGIC-Itch was not collected at baseline.

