### **7.2. Laboratory Evaluations**

Laboratory data collected during the study will be analyzed and summarized using both quantitative and qualitative methods. Summaries of laboratory data will be provided for the Safety Analysis Set and will include data collected up to the last dose of study drug plus 7 days for participants who have permanently discontinued study drug, or all available data at the time of the database snapshot for participants who were ongoing at the time of an interim analysis. The analysis will be based on values reported in conventional units. When values are below the LOQ, they will be listed as such, and the closest imputed value will be used for the purpose of calculating summary statistics as specified in [Section 3.7](#). Hemolyzed test results will not be included in the analysis, but they will be listed in by-participant laboratory listings.

A by-participant listing for laboratory test results will be provided by participant ID number and time point in chronological order for hematology, serum chemistry, and urinalysis separately.

No formal statistical testing is planned.

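### SAP 7.3 lets postpartum (F2) weight and vital signs fall into the later weekly rows and the weight minimum, and leaves out the protocol's summary of potentially clinically significant vital signs (minor)

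*SAP*

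**What the plan says.** - **Weight and vital signs.** SAP 7.3 lists the baseline value, the value and change at each postbaseline time point, and the "Postbaseline minimum value", plus a by-participant listing. It states no last date for inclusion. On unscheduled readings it says only this: "Body weight and vital signs measured at unscheduled visits will be included for the baseline value selection".
- **Laboratory data.** SAP 7.2 does set a cut. Its summaries "will include data collected up to the last dose of study drug plus 7 days for participants who have permanently discontinued study drug".
- **Windows.** SAP Table 2 names weight and vital signs. Week K covers Days 7K−2 to 7K+4, with no last week. SAP 3.8.2 gives one exemption: "A notable exception to the analysis visit windows below is the end of treatment/date of delivery". F2 is not mentioned.
- **Schedule.** Protocol Table 1 collects weight and vital signs at F2, a clinic visit 28 days (±3) after delivery. Treatment ends on the day of delivery (protocol 4.1).
- **Threshold summary.** Protocol 10.4.2.3 says of vital signs that "those meeting criteria for potentially clinically significantly abnormal criteria for each measurement will be summarized with descriptive statistics". The sentence sits in the laboratory section. Protocol 10.4.2.2, the vital-signs section, asks only for descriptive summaries by visit and change from baseline. Neither document gives cut-offs.
- **Versions.** SAP Section 1 says that it is based on protocol Version 1 (14 October 2020). SAP 7.6 declares no deviation from the protocol's safety analyses.

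**The concern.** A row labelled Week 8 in a table of maternal weight or blood pressure will be read as eight weeks on treatment. Under the rules as written, it also holds women who delivered about four weeks earlier and are off drug. The protocol (4.3.2.1) says that "relatively few participants in this study will be expected to remain on treatment beyond 3 weeks", so the late rows contain few on-drug readings to dilute the postpartum ones. The weight minimum has the same fault, because birth itself lowers weight.

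The second gap concerns blood pressure. Protocol 2.1 notes that preeclampsia is more common in ICP, and protocol 5.2 allows adequately managed mild preeclampsia and hypertension at entry. High readings are the direction of interest, yet the one per-woman extreme planned is the lowest reading, and the threshold summary in the protocol was not carried into the SAP.

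**Working it through.** **1. Window rule.** For K = 3, Days 7×3−2 to 7×3+4 are Days 19 to 25, which matches Week 3 in SAP Table 3. Week K ends on Day 7K+4 and Week K+1 starts on Day 7(K+1)−2 = 7K+5, so there are no gaps. Every reading from Day 2 onward falls in some week.

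**2. Where F2 lands.** With delivery on study day D, F2 is on Day D+28±3.

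| Delivery day | Example (baseline → delivery) | F2 days | Row |
|---|---|---|---|
| 8 | 36w0d → 37w0d | 33–39 | Week 5 |
| 22 | 34w0d → 37w0d | 47–53 | Week 7 |
| 29 | 32w0d → 36w0d | 54–60 | Week 8 |
| 36 | 32w0d → 37w0d | 61–67 | Week 9 |
| 50 | 30w0d → 37w0d | 75–81 | Week 11 |

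Week 4 ends on Day 32. An in-window F2 gets there only if D+25 ≤ 32, that is, delivery by Day 7. Exclusion criterion 1 bars women whose delivery within 7 days is already decided, so Weeks 1 to 4 are essentially free of F2.

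**3. Effect of a cut like that in SAP 7.2.** If the last dose is on the day of delivery, the cut is D+7. F2 at D+25 to D+31 lies 18 to 24 days beyond it and would drop out. The delivery visit (day of delivery, +2 days) would remain.

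**4. Share of a weekly row that is F2.** Simulated, with gestational ages assumed:

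| Entry and delivery | Week 7 | Week 8 | Week 9 |
|---|---|---|---|
| Entry mean 33.1–33.7 weeks (SD 2 before capping at 36w0d), delivery mean 37–39 (SD 1) | 25–90% | 54–96% | 78–98% |
| Entry uniform 28–36, delivery uniform 37–39 | 25% | 35% | 54% |
| Entry mean 30.2 (SD 4), delivery mean 37–39 (SD 1) | 5–16% | 10–22% | 16–30% |

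Protocol 4.3.2.1 gives a mean of 33 weeks 4 days at diagnosis in a UK cohort and a median of 34.4 weeks at randomization in a UK trial. Neither is the entry age of this trial.

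**5. Week 8 mean weight change.** Assume a gain of 0.3–0.5 kg/week and a postpartum drop of 2–8 kg. Women still pregnant stand at 8×0.3 = +2.4 to 8×0.5 = +4.0 kg. Women whose F2 falls in Week 8 had gained about 4×0.3 = 1.2 to 4×0.5 = 2.0 kg by delivery. With F2 shares of 54% and 96%:
- 0.46×4.0 + 0.54×(2.0−2) = +1.8 kg
- 0.04×2.4 + 0.96×(1.2−8) = −6.4 kg

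**6. Weight minimum.** With steady gain g, w weeks on treatment and drop L, and ignoring measurement error, the lowest on-treatment change is about +g and the F2 change is g×w − L. F2 is the minimum when L > g(w−1). At g = 0.5 and w = 5 this needs L > 2 kg. A simulation (2 to 5 weekly visits, within-woman SD 0.7 kg, drop SD 1.5 kg) gave:

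| Mean drop | Minimum is postpartum | Minimum at least 2 kg below baseline |
|---|---|---|
| 2 kg | 45–88% | 9–46% |
| 4 kg | 84–99% | 39–85% |
| 6–8 kg | 98–100% | 80–100% |

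With a pre-delivery cut, the last column would be 0.6–1.6%.

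**7. Blood pressure.** A minimum rises only if every reading rises. A simulation took 100 women per arm, 4 visits, mean SBP 112, between-woman SD 8, within-woman SD 7, and a 30–40 mmHg rise, single or persistent, in 10% of one arm and 2% of the other. The minima differed by 0.1–1.0 mmHg, while women newly at or above 140 were 6.9–10.6% against 2.4–3.2%. The planned per-visit group maximum did separate the arms on average (149–164 against 142–150).

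**The case against.** **Hypertension is not lost.** Protocol 9.1.1 does not count as an adverse event "An investigational abnormality (e.g., laboratory parameter, vital sign, or ECG) unless the abnormality is considered clinically significant by the investigator". A reader might infer that new hypertension is counted only at the investigator's discretion. The text does not support that. The exclusion covers isolated abnormal findings. The same section makes new conditions and exacerbations adverse events, and 9.2.1 asks for the diagnosis to be recorded. Diagnosed hypertension or preeclampsia therefore reaches the TEAE tables. High readings also show in per-visit maxima and the listing. What is missing is a count by arm of women who cross a threshold without a recorded diagnosis.

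**No departure over the maximum.** No document requires a per-woman maximum, so its absence is a weakness of choice. The omitted threshold summary is a mismatch with the supplied protocol, but it rests on one sentence in the laboratory section, and SAP 7.6 may be true against Version 1, which was not supplied.

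**Unscheduled readings.** A reader might infer that they are dropped after baseline. SAP 7.3 does not say so, and SAP 3.8.2 assigns observations to windows without excluding them.

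**F2 does little harm.** The early rows are clean, both arms follow one schedule, and SAP 7.3 plans no testing. This stands as a limit on severity. It does not remove the fault, since the late rows and the weight minimum would still be mislabelled. A programmer might keep F2 apart in practice, but SAP 3.8.2 names a single exception and F2 is not it.

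**Conclusion.** The point holds, as minor. That F2 readings enter Week K rows from about Week 5, and enter the weight minimum, follows from the rules as written. How far they distort those summaries depends on assumed entry and delivery ages, weight gain and postpartum drop, none of which the documents give for this trial. The 5–98% spread in row share shows how little can be said about size in advance.

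The documents do not support reading this as a bias between arms. That would need time to delivery to differ by arm. Nor is the primary endpoint touched, because its model stops at Week 3.

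The omission of the threshold summary is established against the protocol supplied. It may be version lag, which explains the gap but leaves it open.

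**What to change.** In SAP 7.3:

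1. Report F2 weight and vital signs as a separate follow-up row, not as Week K.
2. Restrict the postbaseline weight minimum to pre-delivery on-treatment visits. Borrowing the 7.2 rule is not enough, because last dose plus 7 days still admits the weight taken at the delivery visit.
3. Add the protocol 10.4.2.3 summary with SBP/DBP cut-offs fixed before unblinding, for example ≥140/90 and ≥160/110 mmHg (illustrative; the documents give none). Show the number and percentage of women by arm, using all on-treatment readings and saying that unscheduled ones count.
4. Align SAP 7.6 with the current protocol.

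The cost is one SAP paragraph and one extra table, from data already collected.

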### **7.4. Electrocardiogram Results**

ECG data will not be presented in the CSR since ECGs will not be assessed in this study other than as part of the screening process for potential new participants.

## **7.5. Other Safety Measures**

### **7.5.1. Health Utilization Assessments**

Healthcare resource utilization variables include the number and duration of medical care encounters, including surgeries and other selected procedures (inpatient and outpatient), the dates and duration of hospitalization (total days or length of stay, including duration by wards [e.g., intensive care unit]), the number and type of diagnostic and therapeutic tests and procedures, and outpatient medical encounters and treatments (including physician or emergency department visits, tests and procedures, and medications). Descriptive statistics including number of observations, mean, 95% CI on the mean, median, minimum, and maximum will be presented by visit for continuous variables. For categorical variables, the number and proportion of participants will be presented.

### **7.5.2. Newborn Safety Assessments**

The number and percentage of participants who experienced AEs described below will be provided and summarized by SOC and PT unless otherwise indicated:

- TEAEs
- TEAEs of Grade 3 or higher (by SOC, PT and maximum severity)
- Serious TEAEs

Furthermore, all AEs reported within newborns will be listed separately.

## **7.6. Changes From Protocol-Specified Safety Analyses**

There are no deviations from the protocol-specified safety analyses.

## 8. PATIENT-REPORTED OUTCOMES

To evaluate QoL in participants with ICP-associated pruritus treated with volixibat versus placebo on the basis of the following endpoints:

- Change in 5-D Itch scale with 1-week recall from baseline to Week 3 and delivery
- Change in Clinician Scratch Scale (CSS) from baseline to Week 3 and delivery
- Change in EQ-5D-5L from baseline to Week 3 and delivery
- Change in PROMIS fatigue score from baseline to Week 3 and delivery
- Change in PROMIS sleep score from baseline to Week 3 and delivery
- Change in Patient Impression of Severity of Itch (PIS-Itch) from baseline to Week 3 and delivery
- PGIC-Itch at Week 3 and delivery

Because the PROs are administered only at baseline, Week 3, and end of treatment, the change from baseline will be compared between the two groups with use of rank ANCOVA with adjustment for baseline with the Mann-Whitney odds as the estimand. The estimates and CIs can be calculated using the R package sanon ([Kawaguchi and Koch 2015](#)).

Additionally, the difference between treatment groups in the change from baseline at Week 3 and, separately, at delivery, will be evaluated using an ANCOVA model with fixed, categorical effects of treatment group, visit, and treatment group-by-visit interaction as well as the continuous, fixed covariates of baseline and the baseline-by-visit interaction. LS means will be calculated for each treatment group in the model. The difference between volixibat and placebo change from baseline in each outcome variable will be estimated, with the corresponding 2-sided 95% CI constructed for each visit. Change from baseline LS means with standard error, 95% CI for the LS means, p-value for testing if the LS mean is zero, LS mean difference between treatment groups (volixibat minus placebo) with standard error, 95% CI for the LS mean difference, and p-value for testing if the treatment LS means are equal will be calculated for each visit. The number of observations, mean, 95% CI on the mean, standard deviation, median, minimum, and maximum on both the observed and change from baseline values will also be summarized by treatment group for each visit.

For PGIC-Itch, since the PRO is a measure of change without a defined baseline, an ANCOVA model will be used, but will not include fixed covariates of baseline and the baseline-by-visit interaction. The dependent variable will be the PGIC-Itch value.

